3.6.2 Adverse Events of Special Interest

The following are AESIs have been defined in the study protocol:

- Hepatic function abnormality meeting the definition of Hy's Law (HL), which is defined as any increase in alanine transaminase (ALT) or aspartate transaminase (AST) to greater than $3 \times$ upper limit of normal (ULN) and concurrent increase in total bilirubin (TBL) to greater than $2 \times$ ULN.
- Serious hypersensitivity (including Type 1 to 4 hypersensitivity reactions), including anaphylaxis and severe allergic reactions, and immune complex disease.
- Injection site reactions.
- Cardiac events (including angina or myocardial infarction, congestive heart failure, symptomatic atherosclerotic vascular disease, cor pulmonale, or arrhythmia).
- Serious infections (including opportunistic infections and viral reactivations), for example VZ/HSV, EBV/CMV, and TB.
- Gastrointestinal adverse events.
- Malignancy.

AEs will be assigned to a specific category based on investigator's judgement, using a checkbox on the AE CRF page. In addition, an AESI search strategy provided by Patient Safety will also be used to identify AESIs programmatically.

Subjects who meet the following criteria will be summarized by treatment group and separate listings of subjects will be presented:

- ALT/AST > 3 × ULN and any bilirubin > 2 × ULN
- ALT/AST > 5 × ULN for more than 2 weeks
- ALT/AST > 8 × ULN

All other AESIs will be summarized by treatment group and included in separate listings. In addition, the injection site reaction AE will be summarized by the placebo groups.

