5.3 Definition of Adverse Events of Special Interest

An adverse event of special interest (AESI) is one of scientific and medical interest specific to understanding of the investigational product and may require close monitoring and rapid communication by the investigator to AstraZeneca. An AESI may be serious or non-serious. The rapid reporting of AESIs allows ongoing surveillance of these events in order to characterize and understand them in association with the use of this investigational product.

The following AESIs will be particularly monitored in this study (see the Safety Handling Plan for instructions and timing on completing any additional information required for specific types of events related to the categories noted below):

- Hepatic function abnormality meeting the definition of Hy's Law (HL) as described in Section 5.4.12.
- Serious hypersensitivity (including Type 1 to 4 hypersensitivity reactions), for example anaphylaxis and severe allergic reactions, and immune complex disease.
- Injection site reactions.
- Cardiac events (including angina or myocardial infarction, congestive heart failure, symptomatic atherosclerotic vascular disease, cor pulmonale, or arrhythmia).
- Serious infections (including opportunistic infections and viral reactivations), for example VZ/HSV, EBV/CMV, and TB.
- Gastrointestinal adverse events.
- Malignancy.

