5.4.12 Hy's Law

Cases where a subject shows elevations in liver biochemistry may require further evaluation and occurrences of AST or ALT \geq 3 × ULN together with TBL \geq 2 × ULN may need to be reported as SAEs. Please refer to Appendix E for further instruction on cases of increases in liver biochemistry and evaluation of HL.

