Appendix E Actions Required in Cases of Increases in Liver Biochemistry and Evaluation of Hy's Law

E 1 Introduction

This appendix describes the process to be followed in order to identify and appropriately report potential Hy's Law (PHL) cases and Hy's Law (HL) cases. It is not intended to be a comprehensive guide to the management of elevated liver biochemistries. Specific guidance on managing liver abnormalities can be found in Section 5.4.12 of the protocol.

During the course of the study, the investigator will remain vigilant for increases in liver biochemistry. The investigator is responsible for determining whether a subject meets PHL criteria at any point during the study.

All sources of laboratory data are appropriate for the determination of PHL and HL events; this includes samples taken at scheduled study visits and other visits including central and all local laboratory evaluations even if collected outside of the study visits; for example, PHL criteria could be met by an elevated alanine transaminase (ALT) from a central laboratory **and/or** elevated total bilirubin (TBL) from a local laboratory.

The investigator will also review AE data (for example, for AEs that may indicate elevations in liver biochemistry) for possible PHL events.

The investigator participates, together with AstraZeneca clinical project representatives, in review and assessment of cases meeting PHL criteria to agree whether HL criteria are met. HL criteria are met if there is no alternative explanation for the elevations in liver biochemistry other than drug-induced liver injury (DILI) caused by the investigational product.

The investigator is responsible for recording data pertaining to PHL/HL cases and for reporting AEs and SAEs according to the outcome of the review and assessment in line with standard safety reporting processes.

E 2 Definitions

E 2.1 Potential Hy's Law

Aspartate transaminase (AST) or ALT \geq 3 × upper limit of normal (ULN) **together with** TBL \geq 2 × ULN at any point during the study following the start of investigational product irrespective of an increase in alkaline phosphatase (ALP).

E 2.2 Hy's Law

AST or ALT \geq 3 × ULN **together with** TBL \geq 2 × ULN, where no other reason, other than the investigational product, can be found to explain the combination of increases; eg, elevated ALP indicating cholestasis, viral hepatitis, or another drug.

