For PHL and HL, the elevation in transaminases must precede or be coincident with (ie, on the same day) the elevation in TBL, but there is no specified timeframe within which the elevations in transaminases and TBL must occur.

E 3 Identification of Potential Hy's Law Cases

In order to identify cases of PHL, it is important to perform a comprehensive review of laboratory data for any subject who meets any of the following identification criteria in isolation or in combination:

- ALT \geq 3 × ULN.
- AST \geq 3 × ULN.
- TBL \geq 2 × ULN.

When a subject meets any of the identification criteria, in isolation or in combination, the central laboratory will immediately send an alert to the investigator (also sent to sponsor study representative).

The investigator will also remain vigilant for any local laboratory reports where the identification criteria are met, where this is the case the investigator will:

- Request a repeat of the test (new blood draw) by the central laboratory without delay.
- Complete the appropriate unscheduled laboratory case report form (CRF) module(s) with the original local laboratory test result.

When the identification criteria are met from central or local laboratory results the investigator will without delay:

• Determine whether the subject meets PHL criteria (see Section E 2) by reviewing laboratory reports from all previous visits (including both central and local laboratory results).

E 4 Follow-up

E 4.1 Potential Hy's Law Criteria Not Met

If the subject does not meet PHL criteria the investigator will:

- Inform the study representative that the subject has not met PHL criteria.
- Perform follow-up on subsequent laboratory results according to the guidance provided in the study protocol.

E 4.2 Potential Hy's Law Criteria Met

If the subject does meet PHL criteria the investigator will:

- Notify the sponsor study representative who will then inform the study team.
- Within 1 day of PHL criteria being met, the investigator will report the case as an SAE of PHL; serious criteria 'Important medical event' and causality assessment 'yes/related' according to clinical study protocol process for SAE reporting.

The medical monitor contacts the investigator, to provide guidance, discuss and agree on an approach for the study subjects' follow-up (including any further laboratory testing) and the continuous review of data. Subsequent to this contact the investigator will:

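### The Hy's Law criterion in SAP 3.6.2 does not match the protocol's: values exactly at a limit fail both SAP rules, and the handling of a later bilirubin rise is unclear

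*SAP*

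**What the plan says.** **SAP 3.6.2.** The list opens with "The following are AESIs have been defined in the study protocol". The hepatic item is then given as ALT or AST above 3 × ULN and a "concurrent increase in total bilirubin (TBL) to greater than" 2 × ULN. Further down, three laboratory criteria are to be summarized by treatment group and listed by subject. The one that pairs transaminases with bilirubin is "ALT/AST > 3 × ULN and any bilirubin > 2 × ULN". All other AESIs get their own summaries, so the hepatic AESI appears to be tabulated through these laboratory criteria. AESIs are also assigned by an investigator checkbox and by a programmed search strategy.

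**Protocol.** Section 5.3 defines the hepatic AESI by reference to Section 5.4.12, which says that "AST or ALT \geq 3 × ULN together with TBL \geq 2 × ULN may need to be reported as SAEs" and sends the reader to Appendix E. Appendix E 2 gives the same inclusive limits, counted after the start of investigational product. It adds that "the elevation in transaminases must precede or be coincident with" the bilirubin rise and that "there is no specified timeframe within which the elevations in transaminases and TBL must occur". It separates Potential Hy's Law, which is biochemistry only, from Hy's Law, "where no other reason, other than the investigational product, can be found to explain the combination of increases".

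The SAP version history records the added search strategy in 3.6.2. It gives no reason for a different hepatic rule.

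**The concern.** A SAP that says it reproduces a protocol definition should yield the same set of subjects. Here it differs in three respects:

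- **Limits.** The protocol includes values at 3 × and 2 × ULN; the SAP excludes them.
- **Timing.** The protocol sets an order and no time limit. The SAP definition asks for concurrency. The SAP listing criterion states neither order nor timing.
- **Label.** The SAP uses the name Hy's Law for a biochemical rule that Appendix E calls Potential Hy's Law.

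At stake is whether the laboratory-based hepatic summary shows every subject who meets the protocol's biochemical rule. Such subjects are usually rare and are looked at one by one, so the rule that selects them should be unambiguous and the same in both documents.

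**Working it through.** The plan gives no figure to reproduce. The check writes the rules out and applies them to the same constructed subjects.

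**Rules** (multiples of ULN)

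- *P*, protocol 5.4.12 with Appendix E 2: ALT or AST ≥ 3 on some date, and TBL ≥ 2 on that date or any later one.
- *S*, SAP definition, with 'concurrent' read as the same sample: ALT or AST > 3 and TBL > 2 in one sample.
- *L*, SAP listing criterion, with 'any bilirubin' read as at any time: ALT or AST > 3 at some time and bilirubin > 2 at some time, in any order.

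The readings used in *S* and *L* are assumptions, because the SAP defines neither term. Days 57 and 85 are Visits 8 and 9 (SAP Table 1), and serum chemistry is scheduled at both (protocol Table 7).

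| Constructed subject | P | S | L |
|---|---|---|---|
| ALT 4 and TBL 2.5, same day | yes | yes | yes |
| ALT exactly 3.0 and TBL 2.5, same day | yes | no | no |
| ALT 4 and TBL exactly 2.0, same day | yes | no | no |
| ALT 4 on Day 57, TBL 2.5 on Day 85 | yes | no | yes |
| ALT exactly 3.0 on Day 57, TBL exactly 2.0 on Day 85 | yes | no | no |
| TBL 2.5 on Day 57, ALT 4 on Day 85 | no | no | yes |

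In the two-visit rows the other analyte is below its limit at each visit.

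**Reading the table**

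1. At-limit subjects (rows 2, 3 and 5) fail *S* and *L*. For rows 2 and 3 this does not depend on how 'concurrent' or 'any bilirubin' is read.
2. The lagged subject (row 4) fails *S* and passes *L* only on the any-time reading. If 'any bilirubin' instead means any fraction in the same sample, row 4 fails *L* as well. Protocol 4.3.3 measures direct and indirect bilirubin only when the total exceeds 1.5 × ULN, so that reading is plausible.
3. On the any-time reading, *L* also admits the bilirubin-first subject (row 6), whom the protocol's order rule excludes.

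**Check on nesting.** Take two visits with transaminase values 1, 2, 2.5, 3, 4 and bilirubin values 1, 2, 2.5. This gives 5 × 3 × 5 × 3 = 225 patterns.

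- *P*: if the first transaminase value is ≥ 3 (2 values), bilirubin must be ≥ 2 at either visit (9 − 1 = 8 pairs), with any second transaminase value (5): 2 × 8 × 5 = 80. Otherwise (3 values) both criteria must be met at the second visit (2 × 2 = 4), with any first bilirubin value (3): 3 × 4 × 3 = 36. Total 116.
- *S*: 225 − 14 × 14 = 29, all within *P*. So 116 − 29 = 87 patterns meet *P* but not *S*, and 0 meet *S* but not *P*.
- *L*: (25 − 16) × (9 − 4) = 9 × 5 = 45, of which 3 are bilirubin-first patterns outside *P*. So 45 − 3 = 42 are shared, and 116 − 42 = 74 meet *P* but not *L*.

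On biochemistry, *S* is therefore a strict subset of *P*, while *L* and *P* overlap without either containing the other. The counts depend on the values chosen, which include both limits on purpose. They are logical patterns, not expected numbers of patients.

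**The case against.** The strongest reply is that the SAP sentence does not decide which cases are known. Investigators work from Appendix E. They must report a potential case as an SAE within 1 day and can tick the AESI box, and the search strategy is a further route. Out-of-range laboratory values are flagged in the by-subject listings (SAP 3.6.4). Nothing in the SAP removes an investigator-identified case because it fails the SAP wording. All of this stands, and it limits the point to the laboratory-based summary.

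The reply on timing stands in part. The listing criterion does not repeat 'concurrent' and may catch lagged cases. Protocol 4.3.3 also asks for clinically significant abnormal results to be repeated, preferably within 24 to 48 hours, so draws are not confined to scheduled visits. Under a same-sample rule both values need only exceed their limits together; their peaks need not coincide. But Appendix E accepts any lag and any mix of central and local results, and the SAP does not say which timing it means.

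A reader might infer three stronger conclusions that the documents do not support:

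- *Hepatic cases would be lost from the safety report.* The other capture routes argue against this.
- *Cases with another explanation would be tabulated as Hy's Law.* The laboratory criteria in 3.6.2 do not carry that label. Section 5.4.12, which the AESI definition cites, has no exclusion of other causes; that condition sits in Appendix E 2.2.
- *One omitted subject would alter the hepatic conclusion, or the table must equal the SAE record.* The documents give no expected case count and no hepatic decision rule, and a laboratory-threshold table and a reviewed SAE record are different outputs.

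**Conclusion.** The mismatch is certain on the text, and the SAP is wrong as written when it presents its hepatic rule as the protocol's. The firm consequence is narrow: a subject whose qualifying value is exactly at, and never above, a limit meets the protocol rule and fails both SAP rules. Two further consequences depend on undefined words. A later bilirubin rise fails the definition if 'concurrent' means the same sample, and it is listed only if 'any bilirubin' means at any time. On that last reading the listing also admits bilirubin-first subjects.

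The practical size is probably small, since few subjects should sit exactly at a limit; the documents give no figure for this. The risk is an incomplete or inconsistently selected laboratory-based hepatic summary, with the cases themselves still likely to be in the safety record. The point concerns classification and reporting only.

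**What to change.** In SAP 3.6.2, replace the hepatic wording in both the definition and the paired listing criterion with one rule: after the first dose, ALT or AST ≥ 3 × ULN with TBL ≥ 2 × ULN on the same or any later date, with no time limit. Label this Potential Hy's Law, as in Appendix E. Use the name Hy's Law only for cases reviewed under Appendix E as having no alternative explanation. Remove 'concurrent', and replace 'any bilirubin' with total bilirubin.

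The cost is a wording change and a small programming change. The only downside is that a few more subjects may be listed.

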3.6.3 Deaths and Treatment Discontinuations due to Adverse Events

The number and percent of subjects with deaths and treatment discontinuation due to TEAEs will be summarized by treatment group, and separate listings of subjects will be presented.

3.6.4 Clinical Laboratory Evaluation

Hematology, urinalysis and serum chemistry parameters will be assessed at baseline as well as throughout the study. These laboratory parameters and change from baseline will be summarized descriptively by treatment group and visit. Also, the laboratory measurements will be presented as the number and percentage of subjects above or below the normal range for each laboratory test and shifts from baseline relative to the normal range for each treatment group. For laboratory values reported as lower than the limit of quantification (LLOQ), a value equal to half the limit of quantification will be imputed in the summaries. For each hematology and chemistry parameters, boxplots showing the distribution of each parameter by treatment arm and visit will be provided. All laboratory parameters will be provided in the by-subject listings as reported and values outside of the normal range will be flagged.

3.6.5 Vital Signs

Vital signs will be summarized by treatment group and visit. Change from baseline to post-dose evaluations for vital signs will be summarized in a similar way.

3.6.6 ECGs and Left Ventricular Ejection Fraction

An electrocardiogram (ECG) will be performed to confirm that MEDI3506 does not affect cardiac electrophysiological intervals.

The computerized triplicate 12-lead ECG results and QT intervals (msec) will be summarized descriptively by treatment group and visit for each of the ECG variables collected (heart rate, RR interval, QRS interval, PR interval, QT interval (using both Fridericia's correction: $QTcF[\text{msec}] = QT[\text{msec}]/(RR[\text{sec}]^{1/3})$ and Bazett's correction: $QTcB[\text{msec}] =$

$QT[msec]/(RR[sec]^{1/2})$). For the triplicate 12-lead ECG, an average of 3 reads will be used. Changes from baseline will be summarized by treatment group and visit into 3 categories: increase ≤ 30 msec, $30 \text{ msec} < \text{increase} \leq 60$ msec, and increase > 60 msec. Shift tables for QTc intervals ($QTc \leq 450$ msec, $450 < QTc \leq 480$ msec, $480 \text{ msec} < QTc \leq 500$ msec, $QTc > 500$ msec) will be presented to compare the baseline ECG evaluation and the post-dose evaluations. In addition, descriptive summary of qualitative ECG results by visit will be provided.

Left ventricular ejection fraction, as measured by echocardiogram, will be summarized descriptively by treatment group and visit.

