1.7.2 Secondary Hypotheses

In adult subjects with moderate-to-severe AD:

- AD disease severity and symptoms, as measured by additional endpoints, will be decreased in subjects administered MEDI3506 compared with placebo.
- MEDI3506 will be safe and well tolerated compared with placebo.
- The PK profile will support further clinical development of MEDI3506.
- The immunogenicity profile will support further clinical development of MEDI3506.

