2.2 Secondary Objectives and Associated Endpoints

Table 2 Secondary Objectives and Associated Endpoints

Type	Objective	Endpoint
Efficacy		EASI: Percentage of subjects achieving a 90% reduction from baseline in EASI score (EASI 90) at Week 16.
		 Percentage of subjects achieving a 75% reduction from baseline in EASI score (EASI 75) at Week 16.
	To further assess the effects of MEDI3506 compared with placebo on AD disease severity and symptoms, in adult subjects with moderate-to-severe AD.	 Percentage of subjects achieving a 50% reduction from baseline in EASI score (EASI 50) at Week 16.
		Percentage of subjects achieving an IGA of 0 (clear) or 1 (almost clear) with at least a 2 grade reduction from baseline score at Week 16.
		 Peak pruritus NRS: Percentage of subjects achieving a reduction of ≥ 3 from baseline to Week 16 in weekly mean of daily peak pruritus NRS.
		Peak pruritus NRS: Change from baseline to Week 16 in weekly mean of daily peak pruritus NRS.

Table 2 Secondary Objectives and Associated Endpoints

Type	Objective	Endpoint
		 Skin pain NRS: Change from baseline to Week 16 in weekly mean of daily peak skin pain NRS. SCORAD: Percent change from baseline to Week 16. PGI-S at Week 16. Change from baseline to Week 16 in: % BSA affected by AD. 5-D itch. POEM. DLQI.
Safety	To assess the safety and tolerability of MEDI3506 compared with placebo, in adult subjects with moderate-to-severe AD.	During the treatment and follow-up periods: TEAEs and TESAEs. Vital signs. Safety laboratory analysis. ECGs. The following parameters will be recorded for each ECG: Date and time of ECG. Heart rate (beats/min). QT (ms). Overall evaluation (normal/abnormal). Left ventricular ejection fraction as measured by echocardiogram.
PK	To evaluate the PK of MEDI3506 in adult subjects with moderate-to-severe AD.	Serum MEDI3506 concentration profiles during the treatment and follow-up periods.
Immunogenicity	To evaluate the immunogenicity of MEDI3506 in adult subjects with moderate-to-severe AD.	Incidence of ADA during the treatment and follow-up periods.

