4.8.4.3 Analysis of Vital Signs, ECGs, and Echocardiograms

Vital signs, ECG parameters and left ventricular ejection fraction as measured by echocardiogram will be summarized descriptively.

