3 STATISTICAL METHODS

3.1 General Considerations

In general, unless specified otherwise, baseline is defined as the last non-missing assessment prior to dosing. If the baseline is missing following the above definition, baseline evaluations will not be imputed and will be considered as missing. All safety analyses will be performed on the As-treated population. All PK analyses will be conducted using the PK-population. Immunogenicity evaluation will be based on the As-treated population. All other analyses will be performed on the ITT population unless stated otherwise. All data will be provided in data listings sorted by treatment group and subject number. The placebo CCI groups will be pooled for planned analyses, except where stated otherwise. All tabular summaries will be presented by treatment group. Categorical data will be summarized by the number and percentage of subjects in each category. Continuous variables will be summarized by descriptive statistics including number of subjects, mean, standard deviation (SD), median, minimum, and maximum. All statistical tests will be two-sided at an alpha = 0.1 significance level unless stated otherwise.

Day 1 is the first dosing date. Prior to Day 1, study days will be calculated as (sample collection date – Day 1). After Day 1, study days will be calculated as (sample collection date – Day 1 + 1).

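### SAP 3.6.6 says ECGs will confirm that MEDI3506 does not affect cardiac intervals, but the planned summaries give no placebo difference or confidence interval and cannot support that conclusion (minor)

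*SAP*

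**What the plan says.** The stated purpose, in SAP 3.6.6, is: "An electrocardiogram (ECG) will be performed to confirm that MEDI3506 does not affect cardiac electrophysiological intervals".

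The same section then plans the following:

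- **Values by visit.** "The computerized triplicate 12-lead ECG results and QT intervals (msec) will be summarized descriptively by treatment group and visit", covering heart rate, RR, QRS, PR and QT with both the Fridericia and Bazett corrections.
- **Change.** "Changes from baseline will be summarized by treatment group and visit into 3 categories": an increase of at most 30 msec, over 30 to 60 msec, and over 60 msec.
- **Shift tables.** QTc bands cut at 450, 480 and 500 msec "will be presented to compare the baseline ECG evaluation and the post-dose evaluations".
- **Qualitative ECG results** by visit.

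Protocol 4.8.4.3 says only: "Vital signs, ECG parameters and left ventricular ejection fraction as measured by echocardiogram will be summarized descriptively". SAP 3.1 defines what descriptive means for a continuous variable: "Continuous variables will be summarized by descriptive statistics including number of subjects, mean, standard deviation (SD), median, minimum, and maximum", with all tables presented by treatment group.

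The safety objective in Protocol 2.2 is comparative: "To assess the safety and tolerability of MEDI3506 compared with placebo, in adult subjects with moderate-to-severe AD". The secondary hypothesis in Protocol 1.7.2 is comparative too: "MEDI3506 will be safe and well tolerated compared with placebo". ECGs are listed among the endpoints for that objective.

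**The concern.** To conclude that a drug does not affect an interval, one needs an estimate of the difference from control and a bound on how large it could still be. SAP 3.6.6 provides neither for QTc. The shift tables compare each group with its own baseline. The first change category pools every subject whose QTc fell, stayed level or rose by up to 30 msec, so a moderate shift of the whole distribution leaves most subjects where they were.

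The ECG section is also thinner than its neighbours. SAP 3.6.4 (laboratory), 3.6.5 (vital signs) and 3.6.7 (NT-proBNP) each specify a summary of change from baseline. For ECG intervals, change is named only as categories.

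What is at stake is the wording of the report. Cardiac events including arrhythmia are adverse events of special interest (Protocol 5.3, SAP 3.6.2). A statement that absence of effect was confirmed would have no interval behind it, least of all in the two arms of 18 subjects.

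**Working it through.** **Inputs from the documents.** Neither document states an SD, margin or power for QTc, so there is no QTc figure to reproduce. The group sizes do reproduce. The first 72 subjects at 3:3:3:1:2 give 18, 18, 18, 6 and 12. The remaining 80 at 1:1 add 40 to the top dose and 40 to one placebo group. That gives 58, 18, 18 and pooled placebo 6 + 52 = 58, total 152. SAP 3.1 sets two-sided alpha at 0.10, which corresponds to a 90% interval.

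**Assumptions (not in the documents).** The SD of QTcF change from baseline is 12, 15 or 20 msec. Changes are normal, one visit is considered, and all planned subjects contribute. A true mean shift of 10 msec is used for illustration only.

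**Step 1: precision of a placebo difference.** SE = SD × √(1/n + 1/58), and half-width = 1.645 × SE.

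| SD (msec) | SE, 58 v 58 | 90% half-width | SE, 18 v 58 | 90% half-width |
|---|---|---|---|---|
| 12 | 2.23 | 3.7 | 3.24 | 5.3 |
| 15 | 2.79 | 4.6 | 4.05 | 6.7 |
| 20 | 3.71 | 6.1 | 5.40 | 8.9 |

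**Step 2: what the change categories show under a 10 msec shift.** The share above 30 msec is 1 − Φ(30/SD) on placebo and 1 − Φ((30 − 10)/SD) on drug.

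| SD (msec) | Placebo share | Drug share | Expected counts, top dose v placebo (58 v 58) | Expected counts, lower dose v placebo (18 v 58) |
|---|---|---|---|---|
| 12 | 0.6% | 4.8% | 2.8 v 0.4 | 0.9 v 0.4 |
| 15 | 2.3% | 9.1% | 5.3 v 1.3 | 1.6 v 1.3 |
| 20 | 6.7% | 15.9% | 9.2 v 3.9 | 2.9 v 3.9 |

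At SD 15, 100 − 9.1 = 90.9% of treated subjects still fall in the lowest category.

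**Step 3: how much is lost by categorising.** Divide each expected difference by its own standard error. For the share above 30 msec the SE is √(p1(1 − p1)/n + p0(1 − p0)/58). At SD 15, 58 v 58, this gives (0.0912 − 0.0228)/0.0426 = 1.6. The mean difference gives 10/2.79 = 3.6. For SD 12, 15 and 20 in turn:

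- 58 v 58: categories 1.4, 1.6, 1.6; mean difference 4.5, 3.6, 2.7.
- 18 v 58: categories 0.8, 1.0, 1.0; mean difference 3.1, 2.5, 1.9.

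The categories therefore carry roughly a quarter to three fifths of the signal in the mean.

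**Step 4: what the planned means show.** Mean QTc by group and visit is part of the descriptive summary, so a reader can subtract baseline from post-dose means and then placebo from active. With a true 10 msec shift, the active-minus-placebo difference in mean change is at least 5 msec with probability Φ(5/SE): 99%, 96% and 91% for 58 v 58, and 94%, 89% and 82% for 18 v 58. The precision of that difference cannot be recovered from the tables. The SD of change depends on the within-subject correlation between the two visits, which is not tabulated.

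**The case against.** The strongest reply is that group means are planned. A reader might infer from the wide categories that a relevant QTc shift would usually be missed and then reported as no effect. The documents do not support that. SAP 3.1 puts means by treatment group into the descriptive tables, and Step 4 shows that a 10 msec shift would usually appear there. Even the top-dose category counts would tend to lean the right way (Step 2). Failure rates for a significance test on the counts above 30 msec would not help either, because the SAP plans no such test. Nor does any section give a rule for reading balanced tables as confirmation. This part of the objection stands in full.

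It is also fair that this is a proof-of-concept trial whose laboratory, vital-sign, ECG and ejection-fraction data are all handled descriptively, and that one introductory sentence is not a formal equivalence hypothesis. That limits the severity. It does not make the sentence right: adjacent means without the precision of their difference cannot confirm absence.

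A third reply concerns a margin. Protocol 4.3.2.4 makes every ECG after baseline a single reading, and there are several on-treatment ECG visits with none named for a decision. A pass-or-fail margin at an unnamed visit could replace one overstatement with another. That stands, and it is why the remedy below rests on reporting an interval.

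**Conclusion.** The point holds as a minor one. The sentence in SAP 3.6.6 promises a conclusion that its tables cannot deliver, because there is no placebo difference, no interval and no mean change from baseline for QTc. The change categories are insensitive to a moderate mean shift.

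Under the assumed SDs, the data already planned would bound a single-visit difference to within about 3.7 to 6.1 msec for the top dose and 5.3 to 8.9 msec for each lower dose. These figures rest on assumptions that the documents neither give nor contradict, and on complete data. Missing ECGs would widen the intervals; adjustment for baseline could narrow them.

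The finding does not extend to saying that a real shift would escape notice. Efficacy conclusions are unaffected.

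**What to change.** In SAP 3.6.6:

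1. Replace the wording about confirming no effect with *to assess the effect of MEDI3506 on* these intervals.
2. Add, for QTcF, the mean change from baseline by visit and the difference of each MEDI3506 group from pooled placebo with a two-sided 90% confidence interval. Adjust for baseline QTcF, using the MMRM form of SAP 3.4.1.3 or the ANCOVA form of SAP 3.5.1. Keep the category and shift tables, which serve to find outliers.
3. Report the interval in place of a no-effect statement. If the sponsor wants to judge it against a margin, the margin and the visit are the sponsor's to set before unblinding.
4. Align the reference to triplicate ECG results with Protocol 4.3.2.4, where only the baseline ECG is triplicate and later ECGs are single.

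The cost is a wording change and one extra safety table from data already collected, with no new visits or subjects. The one downside is that for the 18-subject arms the report may have to say that a moderate shift cannot be excluded.
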